11.1. Description of Statistical Methods

Descriptive analysis of safety and reactogenicity outcomes will include all subjects who meet the eligibility criteria, receive at least one vaccination, and for whom safety data are available. Summary tables will be created in which incidence, severity, and relationship to the use of investigational product of individual solicited local and systemic signs, symptoms, or trending unsolicited events are delineated by study group, severity, gender, and overall. Unsolicited AEs and SAEs will be analyzed in a similar fashion.

Descriptive analysis of immunogenicity outcomes will include all subjects who meet the eligibility criteria, receive at least one vaccination, and for whom serological data are available. The primary analysis variable will be the proportion of seropositive subjects (defined as $\text{PsVNA50} \geq 1:20$) at each scheduled time point for which blood samples are taken (eg, Days 0, 28, 56, 84 and 140), and the final overall rate of seroconversion over all scheduled time points to study completion for each study group. Seroconversion is defined as a post-vaccination HTNV- or PUUV-specific titer of $\geq 1:40$, or a minimum four-fold rise compared to baseline titer and all study volunteers will begin the study with a baseline titer < 20 (ie, seronegative). For each study group, a binomial proportion and 95% confidence interval (CI) will be calculated. The secondary analysis variable will be geometric mean titers (GMT), with 95% CIs, of the PsVNA50 for HTNV- and PUUV-specific antibodies at each scheduled time point for which blood samples are taken for each study group and over all time points for each study group. GMT, standard errors, and 95% CIs will be calculated using log-transformed titers. For titers below the lower limit of detection (< 20), the value will be transformed to a value equal to the lower limit of detection (ie,

20) divided by the square root of 2, which equals 14.1. Exploratory objectives may evaluate PsVNA80 titers, which may be calculated for informational purposes, and may evaluate PsVNA50 titers against related Seoul and Dobrava viruses.

For hematology and serum chemistry tests, any clinically significant changes from baseline value will be identified. The median, interquartile range, and normal values for each laboratory value (as determined by the contract laboratory) will be reported for each treatment group for each specimen collection point.

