11.1.1. Safety Analyses

Adverse events will be classified by MedDRA system organ class and preferred term, severity, and relationship to study treatment. Serious adverse events will be described. A complete listing of adverse events for each subject will provide details including severity, relationship to study product, onset, duration, and outcome. Laboratory results will be summarized by laboratory parameter, severity, study day, and study arm.

Safety analysis will include data collected from all subjects. Adverse event data will be listed individually (including intervention and outcome) and summarized by body system and preferred terms within a body system for each treatment group. Serious and/or unexpected AEs will also be discussed on a case-by-case basis. For the tabulation of the AEs by body system, a subject will be counted only once in a given body system. For example, a subject reporting nausea and diarrhea will be reported as one subject, but the symptoms will be listed as 2 separate AEs within the class. Therefore the total number of AEs reported within a body system may exceed the number of subjects within the body system reporting AEs.

The total number of AEs reported within body systems between each treatment group will be compared using Fisher's exact test.

Changes in pulse rate, systolic and diastolic blood pressure, weight, and respiratory rate will be compared within each group and among groups using analysis of variance procedures.

Depending upon the sample size, the more common adverse events that may be drug related should be examined for a dose, duration, or demographic relationship, or using other analyses such as standard life-table methods.

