1. PREFACE

The Statistical Analysis Plan (SAP) for “A Phase 1, Randomized Trial to Assess the Safety, Reactogenicity, and Immunogenicity of a Combination HTNV and PUUV DNA Vaccine Candidate Administered by Electroporation” describes and elaborates on the statistical outline provided in the study protocol. Text in the SAP makes reference to the Protocol, and hence, is recommended that the two are read in companion. This SAP overviews the purpose for and nature of the trial methodology. Additionally, tables, figures, and lists that will appear in the final report are previewed.

The SAP is written in the format outlined by the FDA and the International Conference on Harmonisation of Technical Requirements for Registration of Pharmaceuticals for Human Use (ICH) Guidelines, particularly Topics E3, E8, and E9. Furthermore, all work planned and reported for this SAP will follow statistical practice guidelines published by the American Statistical Association and the Royal Statistics Society.

The SAP is organized as follows: Sections 3-5 will review the study design, Sections 6-7 will cover general statistical considerations and subject disposition, Sections 8-9 will discuss in detail the statistical analysis methods, and Section 10-11 will cover reporting conventions and technical details. The Appendices are comprised of Appendix I: Tables; Appendix II: Figures; and Appendix III: Listings. Deviations from this SAP will be discussed and justified in the final CSR.

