8. SAFETY EVALUATION

Safety analysis will include data collected from the Safety Population. Adverse event data will be listed individually (including intervention and outcome) (Listings 1.11.1, 1.11.2, and 1.11.3) and summarized by body system and preferred terms within a body system for each treatment group. Serious and/or unexpected AEs will also be discussed on a case-by-case basis. For the tabulation of the AEs by body system, a subject will be counted only once in a given body system. For example, a subject reporting nausea and diarrhea will be reported as one subject, but the symptoms will be listed as two separate AEs within the class. Therefore the total number of AEs reported within a body system may exceed the number of subjects within the body system reporting AEs. Tables 4.1 and 4.2 will present data about which groups ever experienced adverse effects.

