A complete listing of adverse events for each subject will provide details including severity, relationship to study product, onset, duration, and outcome. Laboratory results will be summarized by laboratory parameter, severity, study day, and study group. Figures 1.3 and 1.4 will present details of adverse effects, by group and visit number. Tables 2.1 to 2.3.4 present data about adverse effects.

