8.5.4. Unexpected Adverse Events or Unexpected Suspected Adverse Reaction

An adverse event or suspected adverse reaction is considered "unexpected" if it is not listed in the investigator brochure or is not listed at the specificity or severity that has been observed; or, if an investigator brochure is not required or available, is not consistent with the risk information described in the general investigational plan or elsewhere in the current application, as amended. For example, under this definition, hepatic necrosis would be unexpected (by virtue of greater severity) if the investigator brochure referred only to elevated hepatic enzymes or hepatitis.

Similarly, cerebral thromboembolism and cerebral vasculitis would be unexpected (by virtue of greater specificity) if the investigator brochure listed only cerebral vascular accidents.

"Unexpected," as used in this definition, also refers to adverse events or suspected adverse reactions that are mentioned in the investigator brochure as occurring with a class of drugs or as anticipated from the pharmacological properties of the drug, but are not specifically mentioned as occurring with the particular drug under investigation.

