	Unrelated												
Headache	Related												
	Unrelated												
Lymphadenopathy	Related												
	Unrelated												
Axillary pain or discomfort	Related												
	Unrelated												
Tachypnea	Related												
	Unrelated												
Fatigue	Related												
	Unrelated												

TABLE 2.3.2: Number and Percentage of Subjects Experiencing Solicited Events by Symptom, Maximum Severity, and Treatment Group

NOTE: Table will be repeated for each injection dose

Symptom	Severity Grade	Group 1 (N=X)		Group 2 (N=X)		Group 3 (N=X)		Group 4 (N=X)		Group 5 (N=X)		Group 6 (N=X)	
		n	%	n	%	n	%	n	%	n	%	n	%
Any Symptom	None												
	1												
	2												
	3												
	Any												
Redness, swelling, bruising, or pain (to include tenderness) at the injection site	None												
	1												
	2												
	3												
	Any												
Fever	None												
	1												
	2												
	3												
	Any												
Myalgia	None												
	1												
	2												
	3												
	Any												

Symptom	Severity Grade	Group 1 (N=X)		Group 2 (N=X)		Group 3 (N=X)		Group 4 (N=X)		Group 5 (N=X)		Group 6 (N=X)	
		n	%	n	%	n	%	n	%	n	%	n	%
Headache	None												
	1												
	2												
	3												
	Any												
Lymphadenopathy	None												
	1												
	2												
	3												
	Any												
Axillary pain or discomfort	None												
	1												
	2												
	3												
	Any												
Tachypnea	None												
	1												
	2												
	3												
	Any												
Fatigue	None												
	1												
	2												
	3												
	Any												

TABLE 2.3.3: Number and Percentage of Subjects Experiencing Unexpected Adverse Events or Unexpected Suspected Adverse Reaction Considered Possibly, Probably, or Definitely Related by MedDRA® System Organ Class, Severity, and Treatment Group

Symptom	Severity Grade	Group 1 (N=X)		Group 2 (N=X)		Group 3 (N=X)		Group 4 (N=X)		Group 5 (N=X)		Group 6 (N=X)	
		n	%	n	%	n	%	n	%	n	%	n	%
Any													
[SOC 1]	1												
	2												
	3												
Any													
[SOC 2]	1												
	2												
	3												
Any													

TABLE 2.3.4: Number and Percentage of Subjects Experiencing Unexpected Adverse Events or Unexpected Suspected Adverse Reaction Considered Unrelated or Unlikely Related by MedDRA® System Organ Class, Severity, and Treatment Group

Table follows Table 2.3.3 formatting.

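### SAP shells merge five injection-site reactions into one graded row, and limit the class-level adverse event tables and listing to *unexpected* events where *unsolicited* was probably meant

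*SAP*

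**What the plan says.** **What the text promises.** Protocol 11.1 calls for summary tables in which "individual solicited local and systemic signs, symptoms, or trending unsolicited events are delineated by study group, severity, gender, and overall", and then adds: "Unsolicited AEs and SAEs will be analyzed in a similar fashion". Protocol 11.1.1 states: "Adverse events will be classified by MedDRA system organ class and preferred term, severity, and relationship to study treatment". SAP 8 says adverse event data will be "summarized by body system and preferred terms within a body system for each treatment group", and SAP 8.5 adds: "A complete listing of adverse events for each subject will provide details including severity, relationship to study product, onset, duration, and outcome". Related unsolicited events within 28 days of each injection are a primary endpoint (SAP 3.3).

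**What the shells show.** SAP 1 says the "tables, figures, and lists that will appear in the final report are previewed", so the mock-ups are meant to be the report.
- Tables 2.3.1 and 2.3.2 (Appendix I), repeated for each dose, have one injection-site row covering all five solicited local reactions. Listing 1.11.3 (Appendix III) has one column for them, headed by redness with a footnote for the rest, and one grade column.
- Table 2.3.3 is headed "Number and Percentage of Subjects Experiencing Unexpected Adverse Events or Unexpected Suspected Adverse Reaction Considered Possibly, Probably, or Definitely Related", split by organ class, severity and group. Table 2.3.4 is its counterpart for unrelated or unlikely related events. Listing 1.11.2 is likewise limited to unexpected events.
- SAP 8.5.4 gives *unexpected* its regulatory meaning. An event qualifies "if it is not listed in the investigator brochure or is not listed at the specificity or severity that has been observed".

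**The concern.** Two separate mismatches between text and shells bear on the primary objective.

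The first is pooling. Protocol Appendix C, Table C-1, grades the five local reactions on five different scales. A Grade 3 entry in the pooled row could be pain that stops daily activity, erythema wider than 10 cm, or an unsightly bruise, and the reader could not tell which. Pain is also the commonest of the five in the earlier experience, so the any-grade row may largely track pain and blur route differences in redness, swelling or bruising.

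The second is scope. *Unexpected* and *unsolicited* are different sets. Protocol 10.3.2 directs that eschar, bleeding, tingling or numbness, and pigmentation change be recorded as unsolicited, although the protocol itself attributes them to the devices. If the brochure lists them, a programmer applying SAP 8.5.4 would leave them out of Tables 2.3.3 and 2.3.4 and Listing 1.11.2, and they are not in the solicited tables either.

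**Working it through.** **Part A: how far pooling could mask a difference**

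Inputs, all from the earlier IM study:
- 76 incidents of injection-site pain in 28 of 31 subjects (Protocol 4.4.2.1.2).
- Doses given (Protocol 4.4.2.1): 27 subjects × 3 + 2 × 2 + 2 × 1 = 81 + 4 + 2 = 87.

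The protocol gives no per-dose pain rate, and the tables are per dose, so I bound the average rate *p*:
- Lowest: each affected subject's incidents all fall on one dose, 28/87 = 32.2%.
- Highest: no dose has more than one incident, 76/87 = 87.4%.

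Let *q* be the per-dose chance of at least one other local reaction. If this is independent of pain, the pooled any-grade rate is 1 − (1 − *p*)(1 − *q*). If *p* is the same in both groups, a difference *d* in *q* shows as *d* × (1 − *p*). For *d* = 50 points:
- *p* = 76/87: 50 × 11/87 = 6.3 points.
- *p* = 28/87: 50 × 59/87 = 33.9 points.

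Subjects without pain after a dose, in a group of 12: 12 × 11/87 = 1.5 to 12 × 59/87 = 8.1. In Group 6, with 22: 2.8 to 14.9.

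**Part B: where a non-solicited event would appear, reading the shells literally**

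| Event | Class × severity × relatedness by group | Adverse event listing |
|---|---|---|
| Unexpected, non-serious | Tables 2.3.3/2.3.4 | Listing 1.11.2 |
| Unexpected, serious | Tables 2.3.3/2.3.4 | Listing 1.11.1 (all SAEs), also 1.11.2 |
| Expected, serious | none | Listing 1.11.1 |
| Expected, non-serious | none | none |

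Other shells partly cover the last row:
- Table 2.2 counts unsolicited events as all versus related, with Grade 3 counts and maximum grade, but without organ class. As extracted it has one overall N. SAP 6.1 says data are reported overall and by treatment group, which would supply the group split.
- Table 4.2 gives ever/never by group only.
- Listings 1.6 and 1.9 may carry an event number, without grade, relatedness or outcome. Listings 1.7 and 1.8 hold raw laboratory and vital-sign values.

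**Is the word a slip?** Three observations suggest so. The SAP 4.1.1 halting bullet says *unexpected* where the matching bullet in Protocol 6.6 says *unsolicited*. SAP 8.5.5 introduces Tables 2.3.3 and 2.3.4 as summaries of *solicited* events and in the next sentence calls them *unexpected*. Tables 2.2 and 4.2 use *unsolicited*.

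Whatever the word, Tables 2.3.3 and 2.3.4 stop at organ class, while SAP 8 and Protocol 11.1.1 promise preferred term.

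**The case against.** The best defence of the pooled row is that it follows the plan's own list: SAP 8.5.3 and Protocol 10.3.2 each put the five reactions in one bullet. That stands as an explanation. But those bullets say what is solicited, not how it is tabulated; Protocol 11.1 asks for individual signs and Table C-1 grades them apart. Listing 1.11.3 could be rescued by one row per event with the reaction named, but the shell does not say so. Table 2.3.2 also splits by maximum grade, so severity could still separate groups.

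Three stronger readings are tempting and should not be drawn.
- *Masking is near total.* A reader might take 28/31 = 90.3% and conclude that 50 points shrink to 50 × 3/31 = 4.8. That is the share of subjects ever reporting pain over up to three doses; the tables are per dose, and 4.8 lies outside the per-dose range.
- *No output will grade any single local reaction.* Table 2.1 covers injection pain by group. Its body is not available, so nothing can be asserted about pain there. Its title does not extend to the other four.
- *Expected unsolicited events vanish from the report.* They do not: serious ones are listed whatever their expectedness (SAP 8.6), and Table 2.2 counts the rest with grade and relatedness.

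On scope, the defence is that SAP 8.5.3 describes solicited events as those identified in the brochure, so the authors may have treated everything else as unexpected, making the three listings exhaustive. The body text of SAP 8 and 8.5 already requires complete output. This supports the slip, and I accept it as the likely intent. It does not remove the need to correct the shells, because SAP 8.5.4 supplies a different definition that a programmer can apply as written.

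**Conclusion.** The point holds as a mismatch between the plan's text and its shells, confined to reporting.

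The pooling stands however *unexpected* is read. Tables 2.3.1 and 2.3.2 and Listing 1.11.3 cannot attribute a grade to a specific local reaction. The possible masking cannot be fixed per dose: a 50-point difference would appear as about 6 to 34 points. That range assumes independence of the other reactions from pain, equal pain across routes, and average per-dose pain as in the earlier, lower-dose IM study. If the other reactions occur mainly in subjects who also have pain, less of the difference would show. No ID pain percentage is given, only that acute pain at electroporation occurred in almost all subjects (Protocol 4.4.2.2.2).

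The scope problem is probably a wording slip. Read literally, it leaves non-serious expected unsolicited events without a class-by-severity-by-relatedness table and without an adverse event listing, contrary to SAP 8 and 8.5 and Protocol 11.1.1. What is lost is the detail, not every count. The device reactions are the likely examples, but this depends on the brochure, so the gap cannot be sized. Events exceeding their brochure severity or specificity would still be tabulated.

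A reader might infer from the SAP 4.1.1 bullet that the halting rule itself was narrowed. Protocol 6.6 states it for unsolicited events, so I do not read it that way.

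**What to change.** 1. Give pain, tenderness, redness, swelling and bruising each its own row in Tables 2.3.1 and 2.3.2, and its own graded column in Listing 1.11.3.
2. Populate Tables 2.3.3 and 2.3.4 and Listing 1.11.2 with all unsolicited events. Add preferred term under organ class in the two tables, and flag unexpected events.
3. In SAP 8.5.5, describe these tables and the listing as covering unsolicited events. In SAP 4.1.1, change the halting bullet to *unsolicited* to match Protocol 6.6.

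The cost is SAP text and shell edits. Including the any-symptom block, symptom blocks go from 9 to 13, so Table 2.3.1 grows from 9 × 2 = 18 rows to 13 × 2 = 26, and Table 2.3.2 from 9 × 5 = 45 to 13 × 5 = 65. Listing 1.11.3 goes from one local column to five. No new data are needed, since Table C-1 already grades each reaction separately. Protocol 11 has the SAP finalized before database lock, which is the point by which to make these changes.

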8.1.4. Follow-Up Visits

There will be 9 follow-up visits: Day $2 + 1$ day, Day 14 ± 2 days, Day 30 ± 1 day, Day 42 ± 2 days, Day 58 ± 1 day, Day 70 ± 2 days, Day 84 ± 4 days and Day 140 ± 7 days and D220 Phone Call ± 14 days

The following procedures will be performed during each follow-up visit (some exceptions):

- Review of subject's medical history (including concomitant medications and AE) since previous visit
- Directed physical examination (injection site) if indicated based on the subject's interim medical history

- Take resting vital sign measurement including oral temperature, heart rate, respiratory rate, and systolic and diastolic blood pressure. Subjects must not eat or drink anything hot or cold, or smoke within 10 minutes prior to taking oral temperature.
- Review and collect memory aids (Days 14, 42, 70)
- Collect approximately 12.5 to 72.5 mL (depending on the scheduled visit day, see [Table 4](#)) of whole venous blood for the determination of:
 - CBC (WBC, Hb, platelets) with differential (Days 14, 42, and 70 only)
 - Glucose, Cr, AST, ALT, total bilirubin, (Days 14, 42, and 70)
- Collect blood for determination of HTNV- and PUUV-specific antibodies as measured by PsVNA assay (Days 84 and 140)
- Collect approximately 50 mL of blood for future research on Day 84 only
- Collect blood sample for determination of pregnancy test (Day 140 only)
- Perform ECG as last assessment of cardiac normality (Day 140 only)

Day 140 will be the final scheduled in-clinic visit for all subjects

Serious Adverse Event Final Telephone Follow Up Visit

There will be a scripted telephone follow up visit conducted at Day 220 ± 14 days.

- Review and collection of serious adverse events occurring since last visit conducted at Day 140.

Early Termination Visits

If a subject leaves the study early (see also Section [7.5](#)), procedures pertaining to Day 140 in the follow-up visit section (Section [8.1.4](#)) will be followed:

- Review of subject's medical history (including concomitant medications and AE) since previous visit
- Directed physical examination (injection site) and resting vital signs check (oral temperature (no recent hot or cold beverages or smoking), heart rate, respiratory rate, and systolic and diastolic blood pressure)
- Review and collection of any remaining memory aids
- HTNV- and PUUV-specific antibodies (PsVNA50 for final visit)
- Serum sample collection for determination of pregnancy test
- Perform ECG

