9.3.2. Determining Neutralizing Antibody Titers of Study Subjects

Sera for immunogenicity testing will be collected on Days 0, 28, 56, 84 and 140. Samples will be analyzed as described in Section 9.2. All PsVNA50 titers will be reported to the PI after the final titer has been determined and have completed all USAMRIID quality assessments.

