5. SAMPLE SIZE CONSIDERATIONS

Because this is a pilot study, all analyses are exploratory. The group sample sizes of up to 12 subjects thus were chosen without the intention that group differences will be detected with a sufficient power.

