6. GENERAL STATISTICAL CONSIDERATIONS

6.1. General Principles

The following descriptive statistics will be reported for all continuous variables: sample size (N), mean, median, standard deviation, first quartile, third quartile, maximum, and minimum. For categorical variables, sample size (N), frequency, and percentage will be reported. In addition, data will be reported overall and by treatment group.

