6.4. Missing Data

No imputations for missing data are planned. For analyses that require study completion, such as the final overall rate of seroconversion for all subjects, subjects who withdrew before the study completion will be excluded.

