9. IMMUNOGENICITY

Descriptive analysis of immunogenicity outcomes will include all subjects who meet the eligibility criteria, received at least one vaccination, and for whom serological data is available. The primary analysis variable is the proportion of seropositive subjects ($\text{PsVNA50} \geq 1:20$) at each scheduled time point (e.g., Days 0, 28, 56, 84, 140, and 220) (Table 3.1), and the final overall rate of seroconversion over these timepoints. Additionally, the proportion of subjects to ever reach seropositivity will be provided at each scheduled time point for which blood samples are taken (Table 3.2). Duration of seropositivity is presented in Table 3.3. For each study group, a binomial proportion, and corresponding 95% CI will be calculated. Chi-squared test or Fisher's exact test will be used to examine the association between group and each binary outcome of interest. Figures 1.1 and 1.2 will present percentages of subjects with seropositivity and seroconversion, by time point by group.

The secondary analysis variable is geometric mean titers, with 95% CIs, of the PsVNA50 for HTNV and PUUV specific antibodies at each scheduled time point (e.g., Days 0, 28, 56, 84, 140, and 220), and will be presented in Figure 1.5. Geometric mean titers, standard errors, and 95% CIs will be calculated using log-transformed titers, titers below the lower limit of detection (<20) will be transformed to a value equal to the lower limit of detection divided by the square root of 2 ($20/\sqrt{2} = 14.1$ Hornung & Reed (1990) (Table 3.4). PsVNA80 titers may be calculated from existing data for information. The reciprocal of the dilution that results in an 80% decrease in luciferase activity is the PsVNA80 titer. PsVNA using other hantavirus PsV (eg, Seoul virus, Dobrava virus) may also be performed to evaluate levels of cross-neutralizing antibodies. Additionally, Fisher's exact test will be used to examine the difference in the proportion of participants to ever seroconvert between each two groups (Table 4.3).

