TABLE 3.1: Proportion of Seropositive Subjects at Each Blood Collection Time Point

Collection Point	Group 1 (N=X)		Group 2 (N=X)		Group 3 (N=X)		Group 4 (N=X)		Group 5 (N=X)		Group 6 (N=X)	
	n	%	n	%	n	%	n	%	n	%	n	%
1	x	xx										
	[x,x]		[x,x]		[x,x]		[x,x]		[x,x]		[x,x]	
2												
3												
4												
5												
6												
7												

Note: 95% confidence intervals for sample proportion in brackets

TABLE 3.2: Proportion of Subjects that Ever Seroconverted at Each Blood Collection Time Point

Collection Point	Group 1 (N=X)		Group 2 (N=X)		Group 3 (N=X)		Group 4 (N=X)		Group 5 (N=X)		Group 6 (N=X)	
	n	%	n	%	n	%	n	%	n	%	n	%
1	x	xx										
	[x,x]		[x,x]		[x,x]		[x,x]		[x,x]		[x,x]	
2												
3												
4												
5												
6												
7												

Note: 95% confidence intervals for sample proportion in brackets

TABLE 3.3: Duration of Seropositivity if Ever Seroconverted

	Group 1 (n=x)	Group 2 (n=x)	Group 3 (n=x)	Group 4 (n=x)	Group 5 (n=x)	Group 6 (n=x)
Mean						
Standard Deviation						
95% CI for Mean						
1st Quartile						
Median						
3rd Quartile						
Min						
Max						

TABLE 3.4: Geometric Mean Titers of the PsVNA50 at Each Blood Collection Time Point

Collection Point	Group 1 (N=X)		Group 2 (N=X)		Group 3 (N=X)		Group 4 (N=X)		Group 5 (N=X)		Group 6 (N=X)	
	μ	SD										
1	x	x	x	x	x	x	x	x	x	x	x	x
	[x,x]		[x,x]		[x,x]		[x,x]		[x,x]		[x,x]	
2												
3												
4												
5												
6												
7												

Note:

- μ = mean; SD = standard deviation
- 95% confidence intervals for sample proportion in brackets

TABLE 4.1: Safety Analysis Group Comparison: Ever Experienced Solicited Adverse Events

Group:	1	2	3	4	5	6	P-value ¹
N=	x	x	x	x	x	x	
% Reporting	xx	xx	xx	xx	xx	xx	
(95% CI)	(x,x)	(x,x)	(x,x)	(x,x)	(x,x)	(x,x)	
Pair 1	•	•					x
Pair 2		•	•				x
Pair 3				•	•		x
Pair 4	•				•		x
Pair 5		•			•		x
Pair 6		•				•	x
Pair 7			•		•		x

¹P-value obtained from a two-sided Fisher's exact test

TABLE 4.2: Safety Analysis Group Comparison: Ever Experienced Unsolicited Adverse Events

Group:	1	2	3	4	5	6	P-value ¹
N=	x	x	x	x	x	x	
% Reporting (95% CI)	xx (x,x)	xx (x,x)	xx (x,x)	xx (x,x)	xx (x,x)	xx (x,x)	x
Pair 1	•	•					x
Pair 2		•	•				x
Pair 3				•	•		x
Pair 4	•			•			x
Pair 5		•		•			x
Pair 6	•				•		x
Pair 7			•		•		x

¹P-value obtained from a two-sided Fisher's exact test

TABLE 4.3: Immunogenicity Analysis: Ever Seroconverted

Group:	1	2	3	4	5	6	P-value ¹
N=	x	x	x	x	x	x	

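### SAP Table 3.3 averages duration of seropositivity without treating subjects still positive at the last serum draw (Day 140) as censored, so its mean and confidence interval do not describe true duration

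*SAP*

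**What the plan says.** SAP Section 9 gives this analysis one sentence: "Duration of seropositivity is presented in Table 3.3". The shell in SAP Appendix I, "TABLE 3.3: Duration of Seropositivity if Ever Seroconverted", has one column per group. Its rows are mean, SD, 95% CI for the mean, first quartile, median, third quartile, minimum and maximum. It has no row for the number of subjects still positive when sampling stopped. Neither document says when seropositivity starts or ends for this table.

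Two general SAP sections come near the question without answering it.

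- SAP 6.1 ("The following descriptive statistics will be reported for all continuous variables") lists N, mean, median, SD, quartiles and range. It lists no confidence interval; that row comes from the shell.
- SAP 6.4 rules out imputation and says that, for analyses requiring study completion, "subjects who withdrew before the study completion will be excluded". A subject who completes the study and is still positive at the last draw is neither missing nor withdrawn, so this rule does not reach that subject.

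On timing, Protocol 9.3.2 states: "Sera for immunogenicity testing will be collected on Days 0, 28, 56, 84 and 140". Protocol 8.1.4 adds: "Day 140 will be the final scheduled in-clinic visit for all subjects". Day 220 is a telephone contact. SAP Section 9 still lists serology "at each scheduled time point (e.g., Days 0, 28, 56, 84, 140, and 220) (Table 3.1", which does not match the current protocol.

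**The concern.** Duration of seropositivity is a time to loss. For a subject still positive at the last draw, the data show only that the duration is at least as long as the observed span. Averaging such spans as if each had ended gives a mean that is too low, and a CI for that mean does not cover true duration at its nominal rate.

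There is a second effect between groups. Because sampling ends on a fixed study day, a subject who turns positive later has less time in which to be seen positive. Two groups with identical persistence but different onset would show different means, and the slower group would look less durable. The six groups differ in dose, route and valency, so a reader could easily take such a gap as a vaccine effect.

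**Working it through.** The documents state no duration or cap, so there is no planned figure to reproduce.

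**Inputs**
- Serum draws on Days 0, 28, 56, 84 and 140 (Protocol 9.3.2). Subjects are seronegative at baseline, so the first possible positive draw is Day 28.
- Visit windows: Day 28 ± 4 (Protocol 8.1.3) and Day 140 ± 7 (Protocol 8.1.4).
- Last vaccination on Day 56.
- Earlier Phase 1 IM study: 14 of 20 seroconverters still had neutralizing antibody 6 months after the last vaccination (Protocol 4.4.2.1.1).

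**Step 1: nominal caps.** The SAP does not define the span, so take first to last positive draw. The cap is 140 minus the first positive day:

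| First positive | Cap (days) |
|---|---|
| Day 28 | 140 − 28 = 112 |
| Day 56 | 140 − 56 = 84 |
| Day 84 | 140 − 84 = 56 |
| Day 140 | 0 |

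With visit windows the longest possible span is (140 + 7) − (28 − 4) = 123 days. On the SAP's Day 220 schedule it would be 220 − 28 = 192 days.

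**Step 2: model-free size.** If every seroconverter is still positive at Day 140, each tabulated span equals its cap. Moving first positivity from Day 28 to Day 56 changes the mean by 84/112 − 1 = −25%. Moving it from Day 56 to Day 84 changes it by 56/84 − 1 = −33%. Persistence is the same throughout. In a group where all are first positive on Day 56 and stay positive, the shell would nominally show mean 84, SD 0 and a CI of zero width, although no loss has been observed.

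**Step 3: is heavy censoring plausible?** 14/20 = 70%, exact 95% CI 46% to 88%, at 6 months after the last dose. Day 140 is only 140 − 56 = 84 days after the last dose. For IM delivery, many subjects still positive at Day 140 is therefore plausible. That study used a different assay, a different HTNV plasmid and a lower dose. For ID delivery, persistence with these vaccines is unknown.

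**Step 4: illustration with some loss.** Assumption: exponential loss starts at the later of Day 56 and first positivity, with 70% still positive 168 days after that start. P(still positive t days after the start) = 0.70^(t/168). The expected span is the sum, over later draws, of the gap since the previous draw times the probability of still being positive.

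- First positive Day 28: 28 × 1 + 28 × 0.70^(28/168) + 56 × 0.70^(84/168) = 28 + 26.4 + 46.9 = about 101 days.
- First positive Day 56: 26.4 + 46.9 = about 73 days.
- First positive Day 84: 56 × 0.70^(56/168) = about 50 days.

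The falls are about 28% and 32%. If the 168-day persistence is varied from 88% down to 30%, the fall from Day 28 to Day 56 onset runs from 26% to 34%.

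**The case against.** **It is one exploratory descriptive table.** This stands, and it sets the severity. Duration is not among the listed endpoints, no test uses it, and SAP Section 5 says: "Because this is a pilot study, all analyses are exploratory". Table 3.1 and Figure 1.1 already show percent seropositive at each draw, though among all subjects and not only seroconverters. They do not correct Table 3.3.

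**Observed time seropositive during follow-up is a legitimate quantity, and a label would do.** Partly right. A clear label and a count of subjects still positive would remove much of the misreading. But the shell is titled as duration, and it attaches a CI to the mean.

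**The shell also gives median and quartiles.** True, but they are limited by the same schedule when most subjects are still positive.

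**The cap is not caused by the missing rule.** Correct. A reader might infer that a censoring rule would lift the 112-day limit. It would not, because the limit comes from the draw schedule. What the missing rule does is let limited spans be averaged as complete ones. The 112 is also nominal and rests on a first-to-last-positive definition that the SAP does not state.

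**A survival estimate adds little with about 10 subjects per group and four post-baseline draws.** It will be imprecise, which is a reason to keep the revision small. It is not a reason to keep a mean that is bounded by the calendar.

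**Conclusion.** The point holds as a minor one. Following the shell would report truncated spans as complete durations. The mean would be biased low for true duration to the extent that subjects are still positive at their last draw, its CI would not be valid, and a later-converting group would look less durable. The 25% and 33% falls need no model beyond all seroconverters remaining positive at Day 140. The 101, 73 and 50 days rest on the exponential assumption and are illustrative only.

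Three stronger readings are tempting and are not supported.

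- A reader might infer that the choice of most immunogenic formulation or route is compromised. The secondary objective rests on seroconversion, seropositivity and GMT, not on duration.
- A reader might use the 70% as persistence measured from first positivity, and so set a floor on true duration above 112 days. The protocol measures it from the last vaccination, and in a study that differs in assay, plasmid and dose.
- A reader might infer that percent positive at Day 140 depends strongly on time of onset. With loss starting no earlier than Day 56, the illustration gives 84% for onset at Day 28 and at Day 56; only Day 84 differs, at 89%.

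**What to change.** Revise the Table 3.3 shell and add a short definition to SAP Section 9:

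1. Drop the mean, SD and 95% CI for the mean.
2. Define duration as time from the first draw at or above 1:20 to the first later draw below 1:20, right-censored at the last available draw.
3. Per group and per virus (Groups 5 and 6 need both), give the number of seroconverters, the number still positive (censored) at the last draw, and a Kaplan-Meier or Turnbull median, shown as not reached where that applies.
4. Label any raw quartiles, minimum or maximum that are kept as observed span, limited by the Day 140 draw.
5. Optionally add the number and percent of seroconverters still at or above 1:20 at Day 140, with an exact 95% CI.
6. Use the protocol's Day 140 as the last draw in place of the SAP's Day 220.

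The cost is SAP wording and one shell; no new data are needed. The downside is imprecision: medians will often not be reached, and intervals will be wide (7 of 10 still positive would have an exact 95% CI of 35% to 93%).
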